#### Post-release Month 1, Month 2, and Month 3 Sessions

The 1 month and 2 month sessions will take place in-person. The REHN will review the participants risk reduction plan, troubleshoot issues the participant has been having with completing their goals and the risk reduction plan will be revised as needed. The Month 3 session will be in person, as well, to facilitate troubleshooting, data collection, and urine testing. Reminders will be sent as described above for the first intervention session. The Month 3 session will be in person, as well, to facilitate troubleshooting, data collection, and urine testing. Reminders will be sent as described above for the first post-release session. These sessions will be used to monitor and enhance the implementation of the risk reduction plans. The REHN will partner with the participant to consider progress and alter plans, as needed. Specifically, the REHN and the participant will: (1) Review and revise the risk reduction and transitional plan together; and (2) Discuss and address facilitators and barriers to implementing the risk reduction and transitional plans, and connect to services as needed. The REHN will provide fentanyl test strips and condoms during in-person sessions.

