Comparison group: Protocols will be identical to those described for the intervention group, but the comparison group members will not take part in any intervention aside from the naloxone training, including HIV or HCV testing. Risks and benefits will be limited to those pertaining to data collection, as described above.

**Collection of Biological Specimens:** The biological procedures to be used by this study will involve conventional medical research methods that are routine in studies of this type. The potential psychological risks will be discussed with participants during the consent process to assist them in making an informed decision as to whether they wish to participate in this part of the study. First, there is the potential for receiving a "false positive" on HIV/HCV testing. This potential is statistically remote because every positive HIV/HCV test result will be confirmed through a confirmatory test. Second, depression is likely when a subject receives a positive result. Similarly, there are emotional liabilities in some cases associated with receiving a negative test result (relief versus survivor's guilt). In either case, post test counseling will be provided and referral to the appropriate human service resources will be offered. The potential risks for a subject revealing her positive serostatus, or experiencing a breach of confidentiality, will also be discussed during post test counseling. These risks involve loss of employment or insurance, rejection by family or friends, and others. The immediate risks associated with the finger pricks and blood draw are slight pain and local bleeding at the site, and are comparable to those incurred during routine medical care.

**Intervention group participants:** The proposed study has potential benefits. First, individuals will have opportunity to be screened for risk behavior including injection drug use and risky sexual activity and receive feedback on results. Second, the study REHN will share important prevention intervention information with high-risk PWUD during the transition from jail to the community with the overall goal of reducing risk behavior and increasing community service utilization. Third, participants will receive an interactive training with animated

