### Exploratory Quantitative Analysis of START-C2H survey data:

Our community randomized trial consists of clustered data with participants nested within counties. To account for this "doubly-repeated" measures design, we will analyze all results using generalized linear mixed models. The covariance matrix for all observations within a county may be written as the Kronecker product of the compound symmetric covariance matrix for participants nested within county and a 2 by 2 residual covariance matrix for repeated measures nested within participants. Implementing the covariance model can be done in both PROC MIXED (for continuous measures) and PROC GLIMMIX (for categorical measures) in SAS by specifying a random intercept for county, and a compound symmetric residual matrix across time (repeated measures within participant). To estimate change in our primary outcomes due to the intervention we will begin by analyzing models of the following form:  $g(y) = \beta_0 + \beta_1 Time + \beta_2 Int + \beta_3 Time * Int$  where  $g()$  represents the appropriate link function for outcome  $y$ ,  $Time$  is a pre-post indicator variable, and  $Int$  is an indicator for the intervention group. The parameter of primary interest is  $\beta_3$ , the difference in slope between the intervention and control group. While our primary outcomes can be approximated as normally distributed, the link function  $g()$  will be modified as necessary to properly model the distribution for each outcome.

**Missing Data.** We will use multiple imputation to account for non-response over time and potential attrition. Additional augmentation variables found to be predictive of missingness will also be included in the imputation model. Ten imputations will be implemented. Additionally, we will use multiple imputation by chained equations to allow for imputation of non-normally distributed variables. All imputation analyses will be done using PROC MI and PROC MIANALYZE in SAS.

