**Power.** We estimated the statistical power to preliminarily detect a change in our outcomes using PROC GLMPOWER in SAS v9.4., accounting for autocorrelation within participants and nesting within counties. We estimate power for a multivariate model equivalent to our planned repeated measures models previously described. Because these analyses are exploratory (due to the smaller-than-anticipated sample size), we set the alpha to 0.10. Based on existing data, we assume a within-county ICC of 0.05 and a within-person autocorrelation of 0.35. We estimate power for all outcomes as approximately Gaussian. We further assume a type-1 error rate of 0.10, 12 counties, and 20 participants per county. At these sample sizes and with an exploratory p-value=0.10, we achieve statistical power of 0.80 for standardized mean of 0.55, or moderate sized effects with an alpha=0.10.

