Triangulating across qualitative and quantitative findings: We will use joint displays to systematically compare and contrast qualitative and quantitative findings for each intervention component/outcome relationship (e.g., preliminary [i.e.,  $p < 0.10$ ] hypothesis test results about the relationship of receiving FTS to subsequent overdose vs. qualitative grounded theory about this same relationship). When qualitative and quantitative findings both suggest an ameliorative relationship, we will conclude that the available evidence supports a beneficial effect. When both find an adverse relationship, we will conclude that the evidence indicates a harmful effect. When neither suggests a relationship, we will conclude that the evidence indicates no effect. When quantitative and qualitative results diverge, we will return to the qualitative and quantitative data to learn if we can resolve this discrepancy. Qualitative data may illuminate an unexpected confounder for the quantitative hypothesis test. Alternatively, qualitative data may suggest that the intervention only has an effect in one subgroup (e.g., individuals residing in counties with more services) and the quantitative findings reach a null conclusion because the quantitative sample is small, and includes both people who do and do not live in such counties. We will seek to systematically explore all divergences using these tables, and seek to refine relational statements and grounded theories accordingly. We will rely solely on qualitative data to learn whether the intervention effect is attenuated in a subgroup (e.g., women), given that the quantitative sample is underpowered to detect effect moderation.

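### The concordance rule draws benefit-or-harm conclusions for single components, but only the whole package is randomised, so a component could be credited with an effect the design cannot identify

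*Combined protocol and SAP*

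**What the plan says.** **Rule.** The SAP paragraph on triangulating qualitative and quantitative findings plans joint displays for every pairing of an intervention component with an outcome. Its example sets preliminary (p<0.10) "hypothesis test results about the relationship of receiving FTS to subsequent overdose vs. qualitative grounded theory about this same relationship". If both strands point to improvement, the evidence is taken to support benefit; if both point the other way, harm; if neither, no effect. Possible confounding of the quantitative test comes up only as something to look for when the strands disagree.

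**Assignment.** Study Design, COVID-19 Policies, randomises the 12 counties to two groups of six, which swap between intervention and comparison after six months.

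**Model.** The SAP begins with a model containing time, an intervention-group indicator and their product. "The parameter of primary interest is" the coefficient of that product. No component or receipt variable appears.

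**Delivery.** Strips come through intervention sessions: "The REHN will provide fentanyl test strips and condoms during in-person sessions". The first community session also covers naloxone, condoms, HIV/HCV education and testing, planning and referral. Under Potential Risks & Benefits, "the comparison group members will not take part in any intervention aside from the naloxone training". The Records, Privacy, and Confidentiality section lets participants decline any component.

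**Error rate and power.** "Because these analyses are exploratory (due to the smaller-than-anticipated sample size), we set the alpha to 0.10"; and "we achieve statistical power of 0.80 for standardized mean of 0.55".

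**The concern.** The trial can estimate what the package does. It has no randomised contrast that separates one component from the others. A conclusion that strips help or harm would be read by health departments and funders as evidence about strips, when it might reflect navigation, referral or naloxone, or the kind of participant who keeps appointments. Agreement between strands is the case in which the plan draws a conclusion, and it is also the case in which it does not ask about confounding.

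**Working it through.** **Step 1. What a test of receiving strips could be.** The SAP does not specify one. Given assignment and delivery, there are two possibilities.

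- *The arm contrast.* The described comparison condition has no strips, so receipt can be equated with being in the intervention arm. The test is then the package contrast, and the same estimate and p-value would serve for any other component treated in this way.
- *A receipt comparison.* Recipients are set against non-recipients, or more receipt against less. Receipt of strips follows attendance at in-person sessions. Receipt of other components follows choice or need: HIV/HCV testing is opt-in, referral support is fitted to the individual, and Vivitrol depends on interest. None of this is randomised. The share of sessions attended is collected as process data but is not in the model.

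**Step 2. Reproduce the plan's power figure, to see which contrast it belongs to.** Inputs from the SAP's Power paragraph: "12 counties, and 20 participants per county"; "we assume a within-county ICC of 0.05 and a within-person autocorrelation of 0.35"; alpha 0.10; standardised effect 0.55. My assumptions: a two-sided test, six counties against six (120 participants per arm), and analysis of pre-post change.

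- Variance of change = 2(1 − 0.35) = 1.30
- Design effect = 1 + 19 × 0.05 = 1.95
- SE = √(2 × 1.30 × 1.95 / 120) = 0.2055
- Noncentrality = 0.55 / 0.2055 = 2.68
- Power from the noncentral t with 12 − 2 = 10 df = 0.801, against the stated 0.80

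The figure matches a whole-package arm contrast. No power is given for any component test.

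**Step 3. Read that contrast as a strips test when strips do nothing.** Let the rest of the package produce a true effect d. The chance of p<0.10 for the row labelled strips is then the power at d:

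| True effect of the other components (SD) | Chance the strips row reaches p<0.10 |
|---|---|
| 0 | 10% |
| 0.30 | 39% |
| 0.55 | 80% |

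These are for a generic, approximately Gaussian outcome, as the SAP's power statement assumes. They are not predictions for overdose.

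**Step 4. The receipt comparison.** The documents give no attendance rate and no strength of selection, so the bias cannot be bounded from them. As an illustration only, a simulation set the true strips effect to zero and assumed 10 intervention and 10 comparison participants per county, ICC 0.05, county fixed effects, 70% attendance, and attendance rising with motivation (log-odds slope 1.0).

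| Assumed situation | Receipt vs non-receipt, p<0.10 | Within intervention arm, p<0.10 |
|---|---|---|
| Other components worth 0.30 to 0.55 SD in attenders | 71% to 99% | 45% to 87% |
| No intervention effect; motivation shifts outcome by 0.2 to 0.4 SD | 16% to 30% | 21% to 47% |
| Neither | about 10% | about 10% |

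**Step 5. Does the qualitative strand correct this?** Under Study Population, CQI, participant interviewees must have taken part in at least two intervention sessions. They report perceived effects of a bundle they received together, and they were selected on attendance. Their agreement is informative about plausible pathways. It is not an independent check on which component caused a difference.

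**The case against.** Several points on the other side stand.

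- A reader might infer that the plan concludes from p<0.10 alone. It does not. Qualitative agreement is required, the tests are called preliminary, and the analyses are declared exploratory.
- A reader might infer that the SAP fixes an invalid component test. It does not. It says it will begin with the arm model and leaves the component test unspecified.
- A reader might assume that receipt of every component simply tracks attendance. The documents do not support that. Testing and Vivitrol depend on choice or need, and pharmacy capacity is meant to serve the wider community, so comparison participants may also have access.
- A reader might want to count how many component rows would be wrong, or to state the direction of the bias. The documents do not fix the number of rows. They describe strips as handed out at sessions, not supplied on request, so heavier users collecting more is not a documented mechanism.
- Theoretical coding looks for broken pathways, gives strips failing to protect against overdose as an example, and examines participants who do not fit. This happens for each pairing before triangulation.

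These points limit the claim without removing it. Looking for broken pathways in interview data does not supply a randomised contrast. The confounding check is not triggered when both strands agree on the same confounded association. An exploratory label supports a looser alpha, not an effect conclusion about a component. The SAP already shows the needed restraint when it leaves subgroup moderation to the qualitative data alone.

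**Conclusion.** The concern holds in this form: a single component could be credited with a package effect or a selection effect, and nothing in the plan prevents it. It does not follow that this will happen.

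The attribution argument rests on documented features: package-level assignment, one arm indicator, bundled delivery, and a rule applied by component. Its size depends on which test is run. If the arm contrast is reused, an inert component's row reaches p<0.10 about 80% of the time when the rest of the package delivers the planned 0.55 SD. That figure rests on the power inputs and the six-against-six layout that reproduces 0.80, and it covers the quantitative entry only; a conclusion also needs qualitative agreement. If a receipt comparison is used, the simulated rates show that the error can be large, but they rest on assumed attendance and motivation and are not estimates for this trial. The whole-package comparison is not affected by this point.

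**What to change.** Amend the triangulation paragraph of the SAP.

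1. Let the quantitative entry behind any conclusion of benefit or harm be the whole-package arm effect for that outcome, with its interval, and state such conclusions for the package only.
2. Keep the component rows for qualitative pathways and, if wanted, receipt associations, labelled non-randomised and hypothesis-generating. Define receipt and list any adjustment for attendance and baseline covariates.
3. Where the strands agree in a component row, report the finding as *consistent with a contribution of the component*, not as an effect.
4. Consider confounding for every component row, not only when the strands diverge.

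Receipt data need not be removed from the joint display. No new data or participants are needed. The cost is SAP wording, a short specification of any receipt analysis, and giving up component-level effect claims.

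### A null quantitative result plus a null qualitative result is reported as evidence of no effect, with no margin, interval condition or inconclusive category

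*Combined protocol and SAP*

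**What the plan says.** The paragraph on triangulating qualitative and quantitative findings, at the end of the SAP, builds joint displays "for each intervention component/outcome relationship". Each cell compares a hypothesis test, described as preliminary and judged at p < 0.10, with the grounded theory from the interviews. There are four branches:

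- both sources favourable: beneficial effect;
- both adverse: harmful effect;
- neither: "When neither suggests a relationship, we will conclude that the evidence indicates no effect";
- sources diverge: go back to the data.

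The Power paragraph describes the precision available: "Because these analyses are exploratory (due to the smaller-than-anticipated sample size), we set the alpha to 0.10". It then states that "we achieve statistical power of 0.80 for standardized mean of 0.55, or moderate sized effects with an alpha=0.10". That power refers to the Time × Int coefficient β3 of the mixed model, "the difference in slope between the intervention and control group".

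The triangulation paragraph does recognise that size matters. For divergent results it allows that "the quantitative findings reach a null conclusion because the quantitative sample is small". For subgroups it turns to the qualitative data alone, "given that the quantitative sample is underpowered to detect effect moderation". Neither caution is applied to the double null.

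**The concern.** A test that misses p < 0.10 shows only that the data do not exclude zero. Whether they exclude effects worth having depends on the width of the interval, which the rule never consults. The interviews do not repair this: they describe pathways that participants perceive, and the absence of a perceived pathway does not narrow a quantitative interval. The benefit and harm branches need positive findings from both sources. The no-effect branch makes an equally firm statement from two absences.

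What is at stake is the reading of individual components. The SAP's own example is receipt of fentanyl test strips and later overdose. A reader of the joint display could take such a component as shown not to work when the data were merely imprecise. The SAP gives no precision for component tests, and it does not say whether receipt means randomised arm or individual uptake.

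**Working it through.** **Inputs.** From the Power paragraph: 12 counties, 20 participants per county, ICC 0.05, within-person autocorrelation 0.35, alpha 0.10, power 0.80 at 0.55 SD. From Study Design (COVID-19 Policies): two groups of six counties that swap condition after six months. Assumed: a two-sided test (the rule allows both benefit and harm), complete data, a Gaussian outcome, 120 participants per arm.

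**Reproducing the SAP's power.** The SAP says the covariance "may be written as the Kronecker product of the compound symmetric covariance matrix for participants nested within county" and a within-person matrix. With each county wholly in one arm:

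- variance of a pre-post change: 2(1 − 0.35) = 1.30
- design effect: 1 + (20 − 1) × 0.05 = 1.95
- SE(β3) = √(2 × 1.30 × 1.95 / 120) = 0.2055
- noncentral t on 12 − 2 = 10 df: power at 0.55 SD = 0.801, matching the stated 0.80

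**Three readings of precision.**

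(a) *Precision matching the stated power.* Half-width 1.812 × 0.2055 = 0.373 SD. An estimate just short of significance has a CI reaching twice that, 0.745 SD. Re-solving the SE for 0.80 power at 0.55 SD with 10 to 478 df gives SE 0.2057 to 0.2209, half-width 0.373 to 0.364 and limit 0.746 to 0.728.

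(b) *The SAP's SAS specification taken literally* (random county intercept plus compound-symmetric residual). The intercept cancels from pre-post change: SE = √(2 × 1.30 / 120) = 0.1472. Half-width 0.242 (normal) to 0.267 (10 df). Power at 0.55 SD is 0.966 to 0.982, so this does not match the Power paragraph.

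(c) *Crossover layout*, 10 participants per county per condition. County effect shared by both cohorts: SE = √(2 × 1.30 × 0.95 / 120) = 0.1435, half-width 0.236 to 0.260. County effects independent between cohorts, design effect 1 + 9 × 0.05 = 1.45: SE = √(2 × 1.30 × 1.45 / 120) = 0.1772, half-width 0.292 to 0.321.

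| Whole-arm β3 | (a) | (b) | (c) |
|---|---|---|---|
| 90% CI half-width, SD | 0.36–0.37 | 0.24–0.27 | 0.24–0.32 |
| Limit of a just-non-significant result, SD | 0.73–0.75 | 0.48–0.53 | 0.47–0.64 |
| P(p ≥ 0.10), true effect 0.2 SD | 76% | 61–65% | 60–72% |
| true effect 0.3 SD | 61% | 35–40% | 33–53% |
| true effect 0.4 SD | 43% | 14–19% | 13–32% |
| true effect 0.55 SD | 20% | 2–3% | 1–11% |

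Ranges in (b) and (c) run over 10 df to normal, and in (c) also over the two county-effect assumptions. The probabilities in column (a) use 10 df.

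**When the true effect is zero.** Simulation with 2,000,000 draws; with 10 df the estimated SE varies from draw to draw. Given p ≥ 0.10, the CI still reaches 0.30 SD in one direction in 96% of trials under (a) and 66–73% under (b). It reaches 0.55 SD in 35% under (a), 0–4% under (b) and 3–17% under (c) with 10 df.

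**The case against.** Five points can be made for the plan.

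- *The figures concern β3, while the rule governs component/outcome pairs.* True. They show the precision of the only contrast the SAP powers and do not measure the rule's error rate for components. That component precision is unstated gives no support for concluding no effect there.
- *Reading (a) is the least favourable and does not reflect the crossover.* This stands in part. Under (b) and (c) a null usually does exclude 0.55 SD, so leaving open the SAP's own moderate effect is mainly a result of (a). Effects of 0.2 to 0.4 SD remain poorly excluded under every reading.
- *The interviews must also be null.* Correct. They are planned across 48 strata among people with at least two intervention sessions. The joint probability cannot be computed, so the percentages are upper bounds.
- *The wording is soft.* The analyses are exploratory, p < 0.10 appears within an example, and the SAP does not say that intervals will be left out of the display. All true. But 0.10 is the alpha in the Power paragraph, no other criterion is offered, and nothing makes the conclusion depend on an interval.
- *Margins for every outcome are real work.* Agreed. They are needed only if the team wants to be able to claim no meaningful effect.

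**Conclusion.** The concern holds and should be fixed. As written, every double null becomes a conclusion of no effect, and nothing in the statistical section qualifies it. At the planning precision, a non-significant whole-arm result leaves open effects of at least about 0.24 SD under all readings tried. At the precision implied by the SAP's own power statement it can leave open 0.55 SD and more.

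The sizes rest on the SAP's ICC, autocorrelation and sample size, together with the assumed two-sided test, 120 per arm and complete data. They do not extend to component tests or to outcomes with another link, such as overdose. The logical fault does not depend on any of these numbers. The exploratory label and the requirement for null interviews limit the harm but do not remove it.

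**What to change.** Replace the sentence with wording such as:

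> When neither source suggests a relationship, we will report no evidence of an effect and call the result inconclusive, showing the estimate and 90% CI for the quantitative comparison in that cell. We will state that there is no meaningful effect only if that CI lies within a margin fixed before analysis.

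Then:

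- set any margin on the outcome's own scale, because the SAP lets the link function vary by outcome;
- show the estimate and 90% CI beside the p-value in the joint display;
- state for each cell whether the comparison is by randomised arm or by individual receipt, and label receipt comparisons non-randomised and hypothesis-generating;
- use the CI for β3 only for the whole-package contrast.

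The core change is SAP wording and one display column. Randomisation, data collection and the model are untouched. Justifying margins is additional work. The price is fewer definitive conclusions: with a true effect of zero, the whole-arm CI falls inside ±0.55, ±0.40 and ±0.30 SD in about 60%, 20% and 4% of trials under (a), and in 93–96%, 62–72% and 25–31% under (b). Those margins are illustrations; the documents state none.
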